6.6.1 Early Stopping of Follow-up

Participants will be followed up for 18 months from randomisation.

If a participant chooses to discontinue from the study care pathway, they should continue to be followed up as closely as possible to the schedule defined in the protocol, providing they are willing. They should be encouraged and facilitated not to leave the whole trial, even though they no longer wish to comply with the study follow up schedule. If, however, the participant exercises the view that they no longer wish to be followed up either, this view must be respected and the participant withdrawn entirely from the trial. CCTU should be informed of the withdrawal in writing using the appropriate Keralink trial documentation. Data already collected will be kept and included in analyses according to the intention-to-treat principle for all participants who stop follow up early. If a patient is only willing to return for one follow up visit, then this should be the 18 month visit.

Participants who stop trial follow-up early will not be replaced.

6.6.2 Participant Transfers

If a participant moves from the area making continued follow up at their consenting centre inappropriate, every effort should be made for them to be followed at another participating trial centre. Written consent should be taken at the new centre and then a copy of the participant's CRFs should be provided to the new centre. Responsibility for the participant remains with the original consenting centre until the new consent process is complete.

Alternatively if a patient requires general anaesthetic which is not available at one site but is available at another site then a transfer for surgery will be accepted but all subsequent follow up appointments should be conducted at the original recruitment site.

6.6.3 Loss to Follow-up

All participants will be asked to provide contact details for, and consent to contact where necessary, a "best alternative contact" such as a relative or close friend. Every effort will be made to maintain contact with all patients.

6.6.4 Trial Closure

The end of the trial will be defined as when the last patient recruited has reached their 18 month follow up visit, all data chases have been completed and all data queries have been resolved.

The REC and MHRA will be notified within 90 days of the end of the trial. A summary report of the research will be sent to the REC and MHRA within 12 months of the end of the trial.

6.7 Sample Size

We have calculated our sample size as follows:

A difference between the groups in the change in K_{max} of 1.5D from randomisation to 18 months would be viewed as a clinically important difference (based on Wittig-Silva RCT of CXL in adults⁸). A K_{max} increase $>1.5D$ would discriminate a true change in the steepest corneal meridian from measurement artefact and would be visually significant.

A sample size of 46 patients would be required to detect this difference at the 5% significance level with 90% power, assuming a SD of 1.5D. The total sample size has been increased to 60 patients (30/group) to allow for up to 24% loss to follow-up. These estimates are based on 12 and 24 month data reported by Wittig-Silva et al⁸ from which we estimate a pooled SD of the changes of 1.476D.

We expect that on average there will be 10% loss to follow up in both groups. In the study by Wittig-Silva et al, 19% of patients withdrew, crossed over to CXL or had a transplant by 18 months. However, 18% of patients in the control group either received CXL or a transplant. If we specifically adjust the sample size to take account of 10% loss to follow up and up to 20% of the control arm cross-over to CXL or transplant, then our planned total sample size of 60 patients would still provide at least 80% power to detect the clinically important difference. The trial design dictates that children cannot cross over to CXL before 9 months.

6.8 Recruitment and Retention

6.8.1 Recruitment

We aim to recruit a total of 60 patients over the 12 month recruitment period from UK NHS sites as described in section 6.1.1: Moorfields Eye Hospital NHS Foundation Trust, Sheffield Teaching Hospitals NHS Foundation Trust and Royal Liverpool & Broadgreen Hospitals NHS Trust. We expect ~50% patients to be recruited in Moorfields, ~25% in Sheffield and ~25% in Liverpool. Patients attending a consultant clinic in one of the three trial centres in whom progressive keratoconus is confirmed may initially have been referred by an optometrist in the community or an ophthalmologist in a hospital eye clinic. These potential participants will be invited to participate in the Keralink trial and provided further information by consultant ophthalmologist principal investigators or authorized suitably trained members of the clinical care teams in the trial centre.

Screening, recruitment and randomisation will be undertaken by qualified individuals at site, and this will be documented on the site delegation log. Individuals taking consent will have received appropriate training.

We expect to recruit 4-6 patients per month across the three sites.

Screening logs, recruitment rates, cross over rates and loss to follow up rates will be reviewed at monthly meetings of the Trial Management Group. Any barriers to recruitment will be investigated and mechanisms put in place to correct them.

6.8.2 Retention

The follow up period for the Keralink trial is 18 months. All participants will be required to attend clinic at 3, 6, 9, 12, 15 and 18 months from randomisation. However, if a participant first shows signs of progression at the 18 month visit, they will need an additional 21 month visit to confirm progression. A visit window of 28 days has been deemed sufficient to allow for the target population to attend follow up visits without this interfering with their school timetables.

Site teams will attempt to book all follow up visits when the patient attends for treatment and they will also routinely contact the patient or parent/guardian prior to each follow up visit as a reminder.

6.9 Assignment of Intervention

6.9.1 Allocation

6.9.1.1 Sequence generation

Patients will be randomised in a 1:1 ratio to CXL or to standard care, via the Sealed Envelope.com website. Sealed Envelope is a randomisation service provider that provides a proven, reliable and centralised computer generated randomisation system. The system will be custom designed to the trial requirements. This will use minimisation with stratification by (a) treatment centre and (b) whether progression is confirmed in one eye or both eyes at randomisation. A random trial arm allocation will be computer generated. Sealed Envelope will provide the randomised treatment for each participant.

6.9.1.2 Allocation concealment mechanism

On the day of randomisation, delegated staff at site will enter the patient's initials, gender, date of birth, date of consent, eligibility criteria fulfilment, treatment centre, and whether progression is confirmed in one or both eyes into the SealedEnvelope.com secure website, which will then allocate the randomised treatment. The treatment allocation will not be concealed from the investigator and the trial participant, however treatment allocation will be concealed from optometrists or delegated staff obtaining the outcome measures. Usernames and passwords for Sealed Envelope will be provided to site staff during the site activation procedure.

6.9.1.3 Allocation Implementation

The responsibility for enrolling and randomising participants into the trial lies with the Principal Investigator and staff at site.

Individuals at participating centres will be provided with a secure login to the sealedenvelope.com website, according to a delegation of responsibilities log. The users will be required to log into the website and answer eligibility questions before entering stratification data and being permitted to randomise. The randomisation result will be shown directly online, with an email confirmation to the user and also to the Trial Manager.

6.9.2 Masking

Although the initial K_{max} measurement may be performed in the facility from which the patient is referred, at all subsequent examinations K_{max} will be measured 3 times by a masked observer. Due to the nature of the intervention, neither the trial participants nor the treating clinician or site staff will be masked to the treatment allocation, but optometrists performing outcome assessments will be unaware of treatment allocation.

6.9.3 Emergency unmasking

As the trial participants and site clinicians will have access to the treatment allocation, emergency unmasking will not be necessary.

6.10 Data Collection, Management and Analysis

6.10.1 Data collection methods

Each participant will be given a unique trial Participant Identification Number (PIN). Data will be collected at the time-points indicated in the Trial Schedule (Table 1).

Pseudo-anonymised data will be collected from the trial sites using paper Case Record Forms (CRFs) and transferred to CCTU. The data will be entered into the MACRO database by a member of the Keralink trial team and stored on secure servers based at UCL. Training on paper CRF completion and storage for site staff listed on the delegation of responsibilities log will be provided at the site initiation meeting(s).

Data collection, data entry and queries raised by a member of the Keralink trial team will be conducted in line with the CCTU and trial specific Data Management Standard Operating Procedure.

Identification logs, screening logs and enrolment logs will be kept at the trial site in a locked cabinet within a secured room.

Clinical trial team members will receive trial protocol training. All data will be handled in accordance with the Data Protection Act 1998.

6.10.2 Data Management

Data will be entered in the approved Keralink database by a member of the Keralink trial team at CCTU and protected using established CCTU procedures.

Pseudo-anonymised data: Participants will be given a unique trial Participant Identification Number (PIN). Data will be entered under this identification number onto the central database stored on the servers based at CCTU. The database will be password protected and only accessible to members of the Keralink trial team at CCTU, and external regulators if requested. The servers are protected by firewalls and are patched and maintained according to best practice. The physical location of the servers is protected by CCTV and security door access.

The database and coding frames have been developed by the Clinical Trial Manager in conjunction with CCTU. The database software provides a number of features to help maintain data quality, including; maintaining an audit trail, allowing custom validations on all data, allowing users to raise data clarification requests, and search facilities to identify validation failure/ missing data.

After completion of the trial the database will be retained on the servers of UCL for on-going analysis of secondary outcomes.

The identification, screening and enrolment logs, linking participant identifiable data to the Participant Identification Number, will be held locally by the trial site. This will either be held in written form in a locked filing cabinet or electronically in password protected form on hospital computers. After completion of the trial, the identification, screening and enrolment logs will be stored securely by the sites for 5 years unless otherwise advised by CCTU.

6.10.3 Non-adherence and non-retention

Trial teams should encourage patients and the parent/guardians to attend all follow up visits. If a patient or parent/guardian wishes to withdraw consent this should be documented in the Withdrawal CRF. Once consent has been withdrawn follow-up will cease.

If however a patient has been deemed lost to follow up, all effort should be made to encourage that participant to attend all remaining trial visits.

6.10.4 Statistical methods

6.10.4.1 Statistical analysis plan

Patient characteristics at the time of randomisation will be summarised using mean and standard deviation for continuous variables which are approximately normally distributed, median and interquartile range for variables which are not normally distributed, or by frequencies and percentages for categorical variables.

All statistical tests will use a 2-sided p -value of 0.05 unless otherwise specified. All confidence intervals presented will be 95 % and two-sided. A detailed statistical analysis plan will be developed for approval by the Trial Steering Committee and review by the Independent Data Monitoring Committee and finalised before the first statistical analysis of unmasked data. All statistical analyses will be performed using Stata (StataCorp, College Station TX, USA).

6.10.4.2 Statistical Methods – Outcomes

For each patient the eye with the more advanced keratoconus at the time of randomisation will be defined as the study eye for the primary analysis. The analysis of the primary outcome will be performed using a linear mixed model fitted to all K_{\max} values recorded after randomisation. K_{\max} at randomisation, treatment group, follow-up time, the interaction between treatment and time, and the stratifying variables centre and whether each patient has only one eye eligible will be included as fixed effects and patient will be included as a random effect. This analysis is equivalent to modelling the change in K_{\max} adjusting for K_{\max} values at randomisation. Model assumptions will be assessed, and a logarithmic transformation used if this improves normality of the residuals. The impact of missing K_{\max} values due to the unreliability of topography measurements in patients who are unable to abstain from wearing lenses for 7 days pre-examination following rigid contact lens wear will be mitigated by applying appropriate multiple imputation methods to estimate these values.

Similar linear mixed models will be fitted for continuous outcomes such as uncorrected and best corrected visual acuity measured at randomisation and on more than one occasion during follow-up. Uncorrected and best corrected visual acuity will be measured in logMAR using an ETDRS chart at a distance of 4 metres.

In patients for whom both eyes show progression at the time of randomisation, information from both eyes will be included in a secondary analysis including eye as a fixed effect and patient as a random effect.

Cox survival analysis method will be used to estimate time to Keratoconus progression in each treatment group. Analysis will be stratified by the stratifying variables, centre and whether each patient has only one eye eligible, and patients who do not progress during the course of the trial will be censored at their last follow-up visit.

We will also explore how health and visual disability in children and young patients with keratoconus relate to changes in K_{\max} . CHU9D is a nine-question paediatric generic preference based measure of health outcome which provides a descriptive health profile as well as a utility score and has been validated for self-completion in an adolescent population (11-17 years)¹². CVAQC is a 25-item vision specific questionnaire designed for children¹³.

Fisher's exact test will be used to compare proportions.

Two sample t tests or Mann Whitney U tests, depending on the distribution of the data, will be used for continuous outcomes measured only at the end of the trial.

6.10.4.3 *Additional Analyses - Subgroup*

An interaction between the number of eyes with progression at randomisation and CXL treatment will be added to the primary efficacy outcome analysis mixed model to investigate whether the effect of CXL differs between patients who had progression at randomisation in one or both eyes.

We will also investigate possible interactions between treatment effect and ethnicity, family history of Keratoconus and atopy as pre-specified subgroup analyses by adding interaction terms to the regression model for the primary outcome.

6.10.5 **Analysis Population and Missing Data**

The primary analysis will be conducted following the intention to treat (ITT) principle where all randomised patients are analysed in their allocated group whether or not they receive their randomised treatment. However, in the event of cross-over from the randomised arm to the other, we will perform two analyses of the primary outcome, the primary ITT analysis and a per protocol analysis. The per-protocol analysis will exclude any information collected from a patient after cross-over. Any cross-over or other treatment deviations will be summarised with reasons.

An ITT analysis will be performed for all secondary outcomes. The impact of missing data will be mitigated against by incorporating information from earlier timepoints using a mixed model approach.

6.11 **Data Monitoring**

6.11.1 **Independent Data Monitoring Committee**

Details of the roles and responsibilities of the Independent Data Monitoring Committee (IDMC), including membership, relationships with other committees, decision making processes, and the timing and frequency of interim analyses (and description of stopping rules and/or guidelines where applicable) are described in detail in the Keralink DMC Terms of Reference (ToR).

6.11.2 **Interim Analyses**

No formal interim analysis is planned, but reports concerning patient safety and key efficacy outcomes will be prepared for review by the Independent Data Monitoring Committee (IDMC) who may request an interim analysis if a report raises concern.

The IDMC will also be asked to review all the assumptions used for the sample size calculation before the end of recruitment.

6.11.3 **Data Monitoring for Harm**

6.11.3.1 *Safety reporting*

Definitions of harm of the EU Directive 2001/20/EC Article 2 based on the principles of ICH GCP apply to this trial.

Table 1: Adverse Event Definitions

Adverse Event (AE)	Any untoward medical occurrence in a patient or clinical trial participant administered a medicinal product and which does
---------------------------	--

	not necessarily have a causal relationship with this product.
Adverse Reaction (AR)	Any untoward and unintended response to an investigational medicinal product related to any dose administered
Unexpected Adverse Reaction (UAR)	An adverse reaction, the nature or severity of which is not consistent with the applicable product information (eg Investigator's Brochure for an unauthorised product or summary of product characteristics (SPC) for an authorised product).
Serious Adverse Event (SAE) or Serious Adverse Reaction (SAR)	Any AE or AR that at any dose: 
 • results in death • is life threatening* • requires hospitalisation or prolongs existing hospitalisation** • results in persistent or significant disability or incapacity • is a congenital anomaly or birth defect • or is another important medical condition***
Serious Unexpected Serious Adverse Reaction (SUSAR)	A serious adverse reaction, the nature and severity of which is not consistent with the information about the medical product in question set out: 
 • in the care of a product with a marketing authorisation, in the summary of product characteristics for that product • in the case of any other investigational medicinal product, in the investigator's brochure relating to the trial question

* the term life threatening here refers to an event in which the patient is at risk of death at the time of the event; it does not refer to an event that might hypothetically cause death if it was more severe (eg. a silent myocardial infarction)
 
** Hospitalisation is defined as an in-patient admission, regardless of length of stay, even if the hospitalisation is a precautionary measure for continued observation. Hospitalisation for pre-existing conditions (including elective procedures that have not worsened) do not constitute an SAE
 
*** Medical judgement should be exercised in deciding whether an AE or AR is serious in other situations. Important AEs or ARs that may not be immediately life threatening or result in death or hospitalisation, but may seriously jeopardise the participant by requiring intervention to prevent one of the other outcomes listed in the table (eg a secondary malignancy, an allergic bronchospasm requiring intensive emergency treatment, seizures or blood dyscrasias that do not require hospitalisation, or development of drug dependency).
	

Adverse events include the following. These will be recorded in the patient notes but will not be notified to the CCTU:

- An exacerbation of a pre-existing illness
- A condition (regardless of whether PRESENT prior to the start of the trial) that is DETECTED after trial drug administration. (This does not include pre-existing conditions recorded as such at randomisation – as they are not detected after trial drug administration.)

- Any reversible or short-term corneal abnormality, e.g. eye pain prolonged >48 hours, delayed corneal epithelialisation, transient corneal oedema.

Serious AEs:

- Requiring hospitalisation or prolongation of existing hospitalisation;
- Resulting in persistent or significant disability, including (i) corneal stromal scarring subsequent to CXL or secondary to post-CXL corneal infection;
- Is otherwise considered medically significant by the investigator.

Adverse events do not include:

- Pre-existing disease or a condition present before treatment that does not worsen
- Medical or surgical procedures: the condition that leads to the procedure is the adverse event
- Hospitalisation where no untoward or unintended response has occurred e.g. elective cosmetic surgery
- Overdose of medication without signs or symptoms

6.11.3.2 *Other Notifiable Adverse Events*

Pregnancy

Pregnancy is a contraindication to CXL on account of possible confounding effects of hormonal change on corneal shape. Subjects known to be pregnant will not be recruited. If a participant becomes pregnant during follow-up they will not be withdrawn; data will be collected until completion of the follow-up period.

6.11.3.3 *Procedures to follow in the event of female participants becoming pregnant*

Participants, who become pregnant during the trial should be allowed to remain in the trial. The participant should continue to be followed up as detailed above.

6.11.3.4 *Investigator responsibilities relating to safety reporting*

All non-serious AEs and ARs, whether expected or not, should be recorded in the patient's medical notes and reported in the AE CRF and sent to the CCTU within 7days. SAEs and SARs should be notified to CCTU as soon as the investigator becomes aware of the event.

6.11.3.4.1 *Seriousness assessment*

When an AR occurs, the investigator responsible for the care of the participant must first assess whether or not the event is serious using the definition given in Table 1. If the event is classified as 'serious' then an SAE form must be completed and CCTU (or delegated body) notified immediately.

6.11.3.4.2 *Severity or grading of Adverse Events*

The severity of all ARs (serious and non-serious) in this trial should be graded using the Common Terminology Criteria for Adverse Events (CTCAE)

Grade 1 Mild; asymptomatic or mild symptoms; clinical or diagnostic observations only; intervention not indicated.

Grade 2 Moderate; minimal, local or non-invasive intervention indicated; limiting age-appropriate instrumental activities of daily living (ADL)*.

Grade 3 Severe or medically significant but not immediately life-threatening; hospitalization or prolongation of hospitalization indicated; disabling; limiting self-care ADL**.

Grade 4 Life-threatening consequences; urgent intervention indicated.

Grade 5 Death related to AE

*Instrumental ADL refer to preparing meals, shopping for groceries or clothes, using the telephone, managing money, etc.

**Self-care ADL refer to bathing, dressing and undressing, feeding self, using the toilet, taking medications, and not bedridden.

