CXL has been reported to be efficacious in the majority of treated adult eyes in a number of non-randomised studies (including Henriquez et al 2011⁵, Hersh et al 2011⁶) and two randomised controlled trials (RCTs) (O'Brart et al 2011⁷, Wittig-Silva et al 2014⁸) The age range treated in these randomised studies was 21-42⁷ and 16-50⁸ years respectively. In the larger study by Wittig-Silva et al a significant difference in progression of K_{max} between CXL and control eyes was reported: an improvement in CXL-treated eyes with flattening of K_{max} by -1.03 ± 0.19 D compared to an increase in K_{max} for control eyes of $+1.75 \pm 0.38$ D at 36 months.

Data from RCTs are reported in an updated Cochrane review comparing CXL with standard care for Keratoconus⁹. Overall the studies were deemed to be at high risk of bias. Data were not pooled due to differences in measuring and reporting outcomes. There was limited evidence on the risk of progression, data suggested that eyes given CXL were less likely to have an increase in maximum keratometry of 1.5D or more at 12 months compared to eyes given no treatment. Other data reported suggested that on average treated eyes had a less steep cornea (approximately 2D less steep) (mean difference [MD] -1.92, 95% CI -2.54 to -1.30; participants = 94; studies = 1, low quality evidence) and better uncorrected visual acuity (approximately 2 lines or 10 letters better) (MD -0.20, 95% CI -0.31 to -0.09; participants = 94; studies = 1, low quality evidence); but the quality of the evidence was deemed low as it was largely derived from one trial at high risk of bias. The data on corneal thickness were inconsistent. There were no data available on QoL. Adverse effects were not uncommon but mostly transient, including corneal oedema, anterior chamber inflammation and recurrent corneal erosions.

(ii) CXL in children and young patients

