6.5.2 Secondary Outcomes

- a) Keratoconus progression (yes/no) defined as >1.5 dioptre increase in K_{\max}^* from baseline (at randomisation) to 18 months **or** requirement for change from spectacle to rigid contact lenses correction of vision, as the latter precludes reliable topography measures
- b) Time to keratoconus progression
- c) Uncorrected and best corrected visual acuity (measured as logMAR)
- d) Refraction (measured dioptres spherical equivalent, myopia and astigmatism)
- e) Apical corneal thickness measurement (ultrasound) **
- f) Quality of life as assessed by CHU9D and CVAQC questionnaires

* We will use K_{\max} measurements as the indicator of disease progression. The probability is high that K_{\max} increases >1.5 D would discriminate a true change in the steepest corneal meridian from artefact. A change of this magnitude is clinically significant, indicating a likelihood of improved visual acuity with correction of the refractive change; for example benefit from spectacle provision in an eye that previously had good unaided vision, a change in spectacle lens correction, or progression from spectacle wear to contact lens correction. K_{\max} will be measured 3 times by a masked observer at each visit during the trial and the mean value used in analyses.

** Apical corneal thickness measurement:

Biomechanical and ultrastructural studies to date have not been able to demonstrate the mechanisms by which CXL stiffens the cornea. The Keralink study will examine changes in thickness of the cornea by ultrasound as topography measurements do not provide accurate and reproducible thickness measurements. Cone apex thickness measurements will be correlated with changes in corneal shape and visual parameters. This will confirm whether arrest of keratoconus progression following CXL is accompanied by arrest in progressive thinning.

Keratoconus disease progression criteria:

- (i) At six months following randomisation and each subsequent follow up visit, corneal topography in each eye will be reviewed for possible progression, defined as a K_{\max} increase >1.5 D from baseline.
- (ii) Bearing in mind the inter- and intra-test variation in topography analysis, any patient found to have >1.5 D increase in K_{\max} will need to have this confirmed at a subsequent visit (i.e. 3 months later). Participants who have unconfirmed progression at the 18 month follow-up visit will need this confirmed at a further visit at 21 months.

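### Time to progression is to be analysed by a Cox model, but with about 1–5 CXL-arm events likely, Wald inference would be weak or unusable when CXL works best; name a log-rank or likelihood-ratio test and Kaplan–Meier risks instead

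*Protocol*

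**What the plan says.** Section 6.10.4.2 of the protocol states "Cox survival analysis method will be used to estimate time to Keratoconus progression in each treatment group". It continues "Analysis will be stratified by the stratifying variables, centre and whether each patient has only one eye eligible". With three centres and one or both eyes eligible, that makes six strata. Children who do not progress are censored at their last visit.

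Section 6.5.2 defines the event as a K_max rise of more than 1.5 D from baseline, or a move from spectacles to rigid lenses. Topographic progression is looked for from month 6, and a patient who shows it "will need to have this confirmed at a subsequent visit (i.e. 3 months later"; a first rise at 18 months is confirmed at 21 months.

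Section 6.7 plans on "A difference between the groups in the change in K_{max} of 1.5D from randomisation to 18 months", tested "at the 5% significance level with 90% power, assuming a SD of 1.5D". On size it says "The total sample size has been increased to 60 patients (30/group) to allow for up to 24% loss to follow-up". Section 6.10.4.1 sets the general rule: "All statistical tests will use a 2-sided p -value of 0.05 unless otherwise specified". The protocol gives no expected number of progressions, no 18-month mean change under CXL, no rate of lens change, and no test or interval type for the Cox model.

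**The concern.** The event requires steepening, whereas CXL is meant to halt steepening or reverse it. Section 5.1 reports from the adult trial "an improvement in CXL-treated eyes with flattening of K_{max} by" 1.03 D at 36 months, and a mean reduction of 0.4 D in an uncontrolled paediatric series. With 30 children in the arm, very few may progress.

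A Cox hazard ratio with its routine Wald test and interval behaves badly in that situation. With no CXL events there is no finite estimate of the log hazard ratio, and the Wald p-value drifts towards 1 however many controls progress. With one or two CXL events the estimate exists, but the Wald test is still weak. The better CXL works, the less the output would show it.

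The sentence also asks the model for something it does not deliver. A Cox model estimates a hazard ratio between arms. Time or risk in each arm needs a separate estimate, and a stratified fit has a different baseline in each stratum.

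**Working it through.** **1. The plan's own figure.** A two-sample t-test with difference 1.5 D, SD 1.5 D and two-sided 5% has power 0.900 (0.8997) at 22 per arm and 0.912 at 23 per arm, so 46 in total is reproduced. Then 46/0.76 = 60.5, and 60 × 0.76 = 45.6, which agrees with 60 patients and up to 24% loss. No comparable calculation is given for time to progression.

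**2. Expected CXL events, topography only.** Take the 18-month change as normal with SD 1.5 D (section 6.7) and mean m (assumed). Then P(rise > 1.5 D) = 1 − Φ((1.5 − m)/1.5). Multiply by 27 patients (10% loss) to 30.

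| Assumed CXL mean m | z | P(rise > 1.5 D) | Events in 27–30 |
|---|---|---|---|
| 0 D | 1.00 | 15.9% | 4.3–4.8 |
| −0.4 D (paediatric series) | 1.27 | 10.3% | 2.8–3.1 |
| −0.515 D (half the adult 36-month figure) | 1.34 | 9.0% | 2.4–2.7 |
| −1.03 D (adult 36-month figure) | 1.69 | 4.6% | 1.2–1.4 |

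The confirmation rule and dropout lower these counts further (step 4).

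**3. What happens with no CXL events.** Let β be the log hazard ratio, CXL against control. If all events are in controls, each contributes 1/(n₀ + n₁e^β) to the partial likelihood, where n₀ and n₁ are the numbers at risk. Every term rises as β falls, so the maximum lies at β = −∞ and the hazard ratio goes to 0. The information shrinks like e^β, so the standard error grows like e^(−β/2) and β/SE tends to 0.

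Example: six control events, no CXL events, risk sets about equal and no ties.
- Log-rank: expected CXL events 6 × ½ = 3, variance 6 × ¼ = 1.5, χ² = 3²/1.5 = 6.0, p = 0.014.
- Likelihood ratio: 2 × 6 × ln 2 = 8.3, p = 0.004.
- Wald: p tends to 1.

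**4. Simulation.** Inputs from the protocol: 30 per arm, difference 1.5 D, SD 1.5 D, 10% loss, centre shares 50/25/25%, visits every 3 months, confirmation including month 21. Assumed: the CXL mean, 50% with both eyes eligible, the split of the SD between slope and visit noise, and Breslow ties. Lens changes are left out here; 700–800 trials per setting.

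| CXL mean | Mean CXL events | Log hazard ratio non-finite | Wald power | Likelihood-ratio or log-rank power |
|---|---|---|---|---|
| 0 D | 3.5–3.7 | 2–3% | 71–76% | 78–84% |
| −0.4 D | 2.0–2.2 | 10–13% | 51–55% | 72–77% |
| −0.515 D | 1.6–1.9 | 15–20% | 39–43% | 66–74% |
| −1.03 D | 0.8–1.0 | 41–46% | 9–10% | 50–61% |

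A binomial check agrees: with 3.6, 2.1 and 0.9 expected events in 30, P(no event) = (1 − 3.6/30)³⁰ = 2%, (1 − 2.1/30)³⁰ = 11% and (1 − 0.9/30)³⁰ = 40%. A separate simulation over CXL means down to −1.0 D gave non-finite estimates in 1–33% of trials and Wald losses of 3–43 points.

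**5. Lens changes added.** With assumed rates of 10% control and 5% CXL, or 20% and 10%, mean CXL events are 3.6–5.0, non-finite estimates fall to 0.3–2%, and the Wald loss against the likelihood-ratio test is 5–8 points.

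**6. Type I error.** In two null settings the rejection rates were Wald 1–3%, likelihood ratio 4–6% and log-rank about 5%. The extra power of the last two is not bought by inflation.

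**7. Role of the strata.** An unstratified fit gives nearly the same non-finite rates: 8–12% at −0.4 D and 40–47% at −1.03 D. Stratifying costs about 3–8 points of likelihood-ratio power at means from 0 to −0.515 D.

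**The case against.** The strongest reply is that the protocol never names a Wald test. The score test of a stratified Cox model is, apart from ties, the stratified log-rank test, and likelihood-ratio inference comes from the same fit. A detailed SAP is promised before unmasked analysis and could settle the test and a zero-event rule. This stands, and it limits the point to an improvement. It does not remove it: the protocol commits to the Cox model, the routine output of that model fails when CXL works well, and the sentence misdescribes what Cox estimates.

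Second, whether CXL stops progression is also asked by outcome (a), and section 6.10.4.2 compares proportions by Fisher's exact test, which copes with an empty cell: 0/30 against 6/30 gives p = 0.024, and 0/30 against 8/30 gives p = 0.005. This stands too. What is at risk is the time-to-event estimate and its interval, not the progression question as a whole.

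Third, the size depends on inputs that the protocol lacks. The −1.03 D is an adult 36-month figure, while the trial follows children aged 10–16 for 18 months. Lens changes add events at an unknown rate. At the assumed rates in step 5 the problem is small; an assumed 10% control and 3% CXL left 4–31% non-finite across the settings tried.

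A reader might infer that the hazard ratio will often be inestimable on the protocol's own figures, or that six strata are to blame. The documents support neither. Frequent failure needs a CXL mean near −1.0 D and few lens changes, and the cause is the low CXL event count. Rates of 71–86% arise only if the adult trial's ±0.38 and ±0.19 are taken to show a control SD twice the CXL SD, which the protocol does not state.

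**Conclusion.** The point holds as a cheap improvement to a secondary analysis. About 1–5 CXL-arm events are to be expected, with or without modest lens-change rates, under the planning SD and difference and an assumed CXL mean of 0 to about −1.0 D. A hazard ratio of 0 with no usable Wald interval would occur in about 1–3% of trials at 0 D, about 10% at −0.4 D and 33–46% near −1.0 D, and less often with lens changes. If Wald inference is used, the power lost against a log-rank or likelihood-ratio test is about 3–8 points at 0 D or with modest lens-change rates, about 20 at −0.4 D and 40 or more near −1.0 D. Individual trials can fall outside the range of means: the simulated 5–95% range of CXL events was 1–7 at 0 D and reached 9 with lens changes. The primary K_max analysis is not touched.

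**What to change.** In section 6.10.4.2, or in the SAP before unmasked data are analysed:

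- Test time to progression with the log-rank (or likelihood-ratio) test, using the same strata.
- Report Kaplan–Meier progression risk by arm at 18 months, in place of the statement that Cox estimates time in each group.
- Report the Cox hazard ratio with a profile-likelihood interval, and use a Firth-penalised estimate if an arm has no events. Do not rely on the Wald test or interval.

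This costs a sentence or two of text and slightly more analysis code. If the Firth estimate is used, the hazard ratio is shrunk slightly towards 1. Sample size, visits and data collection do not change.
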